Conservatively assuming an OCTAPLEX hemostatic success probability of at least 85% and a Beriplex® P/N (Kcentra) hemostatic success probability of at most 89%, it is planned to enrol 185 patients in each treatment arm, i.e. 370 patients in total.

Assuming a proportion of about 10% randomized patients who were not treated or did not undergo the surgical procedure for administrative reasons; this would ensure that data on at

Study Protocol	CONFIDENTIAL	Version 04
No. LEX-209		19-Jan-2018

least 166 patients per treatment group in the modified ITT (mITT) population will be available for the final statistical analysis as derived from the sample size calculation.

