### 9.2.1 Population for Analysis

The randomized population (RAND) will include all randomized patients irrespective of whether they received treatment. This is the intent-to-treat (ITT) population according to the most rigid definition of ITT.

The safety analysis population (SAF) will include all randomized patients who received at least one dose of IMP. Patients receiving different study treatments than originally randomized will be considered according to the treatment actually received (rather than that of the original randomization).

For further statistical analysis of the efficacy parameters, a modified Intention-to-Treat population (mITT) is defined: All randomized patients who received at least one infusion of IMP, and who had the surgery initiated or for whom the surgery was not initiated for medical reasons related to insufficient coagulation. Patients in whom the surgery was not initiated due to technical reasons/aesthesia/etc (i.e., not related to insufficient coagulation) will be excluded from the mITT, whereas patients in whom the surgery was not initiated for coagulation-related reasons will be considered as treatment failures.

The Per-protocol (PP) population: This analysis population will consist of all patients in the mITT population, excluding patients with major protocol deviations potentially affecting the primary endpoint. The following patients will be excluded:

- Patients who receive an IMP different to the IMP assigned by randomization
- Patients who receive less than 70% of the planned dose
- Patients who significantly violate inclusion/exclusion criteria
- Patients with missing primary efficacy assessment
- Start of surgery more than 5 hours after end of infusion of IMP

A final decision about the classification of protocol deviations as major and minor and their consequences regarding assignment of patients to analysis populations will be made during the blinded data review meetings prior to unblinding of patient cohorts for the interim and final analyses. Decisions and outcome will be approved by the Sponsor.

The analysis of safety will be based on the SAF.

The primary efficacy analysis will be based on all randomized subjects (RAND=ITT).

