Conservatively assuming an OCTAPLEX hemostatic success probability of at least 85 % and a Beriplex[®] P/N (Kcentra) hemostatic success probability of at most 89%, it is planned to enroll 185 patients in each treatment arm, i.e. 370 patients in total.

Assuming a proportion of about 10% randomized patients who were not treated or did not undergo the surgical procedure for administrative reasons this would ensure that data on at least 166 patients per treatment group in the modified ITT (mITT) population will be available for the final statistical analysis as derived from the sample size calculation.

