10.1 Primary efficacy analysis

The primary efficacy variable is the hemostatic efficacy as assessed by the IEAB. The hemostatic efficacy is to be assessed based on objective criteria in the categories 'excellent', 'good', 'moderate' or 'none'. Ratings of 'excellent' and 'good' will be considered as 'effective' hemostasis, while a rating of 'moderate' and 'none' will be considered as 'ineffective' hemostasis. For details on the derivation see CSP Section 7.2.1 (Assessments for Primary Efficacy Endpoints).

The dichotomous 'hemostatic success' variable will be used in the analyses. This variable will be imputed as 'ineffective' under the following two circumstances:

- If hemostatic efficacy value is missing, then hemostatic efficacy will be considered 'none' for the analysis. This can occur in the RAND population if the patient is randomized and not treated (or does not undergo surgery), also in the mITT population if the patient is treated but does not undergo surgery due to insufficient coagulation.
- If patient receives additional coagulation treatment (e.g. PCC, single coagulation factors, plasma) after initial IMP infusion, then hemostatic efficacy will be considered 'none' for the analysis.

To demonstrate that treatment with OCTAPLEX is clinically not inferior to treatment with Beriplex[®] P/N (Kcentra) with respect to hemostatic success, a two-sample, one-sided test of the pair of hypotheses: 20

- H₀: $p_{\kappa} p_0 \ge \delta$ (inferiority) H₁: $p_{\kappa} p_0 < \delta$ (non-inferiority) VS.

will be carried out with a type I error probability of $\alpha = 0.025$ and clinical non-inferiority margin of $\delta = 0.15$. Whereby p₀ and p_K present the probabilities of hemostatic success of OCTAPLEX and Beriplex[®] P/N (Kcentra) respectively.

Farrington's and Manning's test for difference in proportions will be used to assess the primary hypothesis in an interim and in the final analysis. One-sided p-values and the corresponding nominal and repeated confidence intervals for the difference in hemostatic success probabilities will be presented.

The primary analysis will be performed on the RAND population. Additional analyses will be performed using the mITT and PP populations.

All patient data related to the primary efficacy analysis will be listed.

Handling of Missing Data

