12.4 Stopping rules and adaptations

A sequential design with α - and β -spending function according to Hwang, Shi and Cani will be used.

After the interim analysis, a positive outcome for non-inferiority test may be claimed and enrollment may be stopped (after consultation between the IDMC and relevant parties, see section 9.4 of the CSP) if the primary test statistic in the RAND population is greater than the adjusted critical value $z_1 = 2.33$ corresponding to an adjusted significance level of $\alpha_1 = 0.01$ (efficacy stop), as reported in the table below. If a p-value > 0.5 is observed, the study may be stopped for futility (non-binding futility stop). The worst effect of a possible overrunning on the final result will be assessed if the result suggests a termination of the study. Individual patient data relevant to the interpretation of interim results will be listed.

| operational characteristics of Stady Design | | | | | | |
|---|-----------|------------------------|---------|--|--|--|
| | | Significant Boundaries | | | | |
| | n per arm | Z-value | p-Value | | | |
| Interim | 83 | 2.33216 | 0.00985 | | | |
| Final | 166 | 2.07753 | 0.01888 | | | |

Operational Characteristics of Study Design

If study success can be claimed on the interim results, enrollment of additional patients may be discontinued prematurely. In this case, all patients enrolled until a decision to stop the study has been made will be observed until the end of follow-up period. A final analysis and study report including all data collected during the study will be prepared.

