12.5 Documentation of the interim analysis and disclosure of results

The interim analysis will be performed by a statistical team which is independent from the study team.

The results of the interim analysis will be presented to the IDMC. The following statistical summaries and listings will be presented:

- Analysis of patient populations and withdrawal status (Number and percentage of patients in the enrolled population, RAND, SAF, and withdrawals) A statistical summary of important demographic Analysis of patient populations and withdrawal status
- A statistical summary of important demographic and baseline data for the RAND.
- Descriptive statistics and statistical test results including the p-value, point estimates and confidence intervals for the RAND of the primary efficacy variable.
- Descriptive statistics of the secondary efficacy variables
- An analysis of AEs for the SAF. This will include frequency tables of TEAEs and TEAEs assessed by the investigator as related (i.e. any possibly, probably, or definitely related TEAEs) according to primary SOC and preferred term. Serious TEAEs, TEAEs with fatal outcome, and TEAEs resulting in withdrawal from the study will be tabulated using frequency tables if a reasonable number of AEs of this type are observed.
- Frequency tables of TEEs
- Patient listings will be provided for all AEs reported, for patients with SAEs, for all patients with AEs leading to study discontinuation and for all AEs with fatal outcome. The listings will include all patients in the SAF and will show the investigator verbatim Mea Property of Octapt term and the MedDRA coded term simultaneously.

Version: 03 06-Jan-2021

13 Statistical Analyses for Safety Monitoring

The statistical analysis for safety monitoring is specified in a separate IDMC charter.

Property of Octapharma. Do not copy or distribute without written permission.

Version: 03 06-Jan-2021

14 Software

If not stated otherwise, the data will be analysed using SAS Version 9.3 or higher.

Property of Octapharma. Do not copy or distribute without written permission.

15 Abbreviations

| 4F-PCC | Four-Factor Prothrombin Complex Concentrate |
|--------|---|
| AE | Adverse Event |
| BMI | Body Mass Index |
| CI | Confidence Interval |
| CSP | Clinical Study Protocol |
| CSR | Clinical Study Report |
| | |

| | 01 | |
|---|--------|--|
| | CSP | Clinical Study Protocol |
| | CSR | Clinical Study Report |
| | | miss |
| | | OCX |
| | eCRF | Electronic Case Report Form |

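### The stated 80.3% power belongs to 166 mITT patients per arm; the primary test on all 185 randomised per arm has about 73% under the plan's own 10% assumption

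*SAP*

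**What the plan says.** Protocol 9.1 and SAP 3.1 carry the same sample-size table: 166 per group and 80.3% actual power for 89% against 85%, with a margin of 15 points, one-sided 2.5% and one interim at half. The step from 166 to 185 is explained by losses: "Assuming a proportion of about 10% randomized patients who were not treated or did not" have surgery for administrative reasons. After those losses, "data on at least 166 patients per treatment group in the modified ITT (mITT) population will be available" (SAP 3.1).

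The primary analysis uses another population. Protocol 9.2.1 says "The primary efficacy analysis will be based on all randomized subjects (RAND=ITT"; SAP 10.1 says "The primary analysis will be performed on the RAND population". SAP 10.1 scores a missing hemostatic rating as none, hence ineffective, and states whom this affects: "This can occur in the RAND population if the patient is randomized and not treated (or does not undergo surgery".

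SAP 12.4 allows an early claim "if the primary test statistic in the RAND population is greater than the" critical value of 2.33. The design table beneath it lists 83 per arm at the interim and, for the last look, "Final | 166 | 2.07753 | 0.01888". Under SAP 12.2 the interim cohort is the first 185 randomised patients. In SAP 12.5 the only primary-endpoint test listed for the IDMC is the one with "confidence intervals for the RAND of the primary efficacy variable".

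**The concern.** The patients removed to arrive at 166 are not removed from the primary test. They stay in it as failures. This changes three things at once: n rises from 166 to 185 per arm, both success rates fall, and the true difference shrinks slightly. Neither document gives the power of that test, so a reader will take about 80% as the power of the primary analysis.

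The same choice affects the meaning of the margin. If equal fractions are scored as failures in both arms, any difference among treated and operated patients looks smaller in RAND. At the final analysis the mITT and PP tests and the tipping-point analysis address this. At the interim, where non-inferiority may be claimed, the listed package contains no undiluted comparison.

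**Working it through.** **Inputs.** Margin δ = 0.15, overall one-sided α = 0.025, rates 89% and 85%, 166 and 185 per arm, and 10% not treated or operated on (Protocol 9.1, SAP 3.1). Boundaries z = 2.33216 and 2.07753, with the interim at half (SAP 12.4). Missing rating scored as failure in RAND (SAP 10.1). The 3%, 5% and 15% fractions are assumptions chosen to show the range.

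**Test.** Farrington-Manning: Z = (δ − (p̂K − p̂O)) / √[(p̃K(1 − p̃K) + p̃O(1 − p̃O))/n], where p̃K and p̃O are the maximum likelihood estimates constrained to differ by δ. A trial succeeds if Z exceeds 2.33216 at the interim or 2.07753 at the end. Binomial data, 1,000,000 simulated trials per scenario.

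**Reproducing the plan.** Hwang-Shih-DeCani spending with γ = −0.8 gives boundaries of 2.325 and 2.076, close to the SAP table. At 166 per arm and 89/85, simulated power is 80.6% (80.4% with the futility stop); a bivariate normal calculation gives 79.9%. The stated 80.3% is reproduced. The inflation is also right: 166/0.9 = 184.4, rounded up to 185.

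**The primary test.** If a fraction f in each arm is scored as failure, the rates tested are (1 − f) × 89% and (1 − f) × 85%. At f = 10% they are 80.1% and 76.5%.

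| Population, n per arm | f | Rates tested (%) | Power, no futility stop | Power, futility stop |
|---|---|---|---|---|
| mITT, 166 | – | 89.0 / 85.0 | 80.6% | 80.4% |
| RAND, 185 | 3% | 86.3 / 82.5 | 80.7% | 80.5% |
| RAND, 185 | 5% | 84.6 / 80.8 | 78.4% | 78.2% |
| RAND, 185 | 10% | 80.1 / 76.5 | 73.3% | 73.0% |
| RAND, 185 | 15% | 75.7 / 72.3 | 69.6% | 69.3% |

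**Why power falls although n rises** (simple unpooled variance, for illustration):
- mITT: variance term 0.89 × 0.11 + 0.85 × 0.15 = 0.2254; SE = √(0.2254/166) = 0.0368; distance to the margin 0.15 − 0.04 = 0.11, or 2.99 SE.
- RAND at 10%: variance term 0.801 × 0.199 + 0.765 × 0.235 = 0.3392; SE = √(0.3392/185) = 0.0428; distance 0.15 − 0.036 = 0.114, or 2.66 SE.

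The variance term grows by about 50% and n by about 11%.

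**Other true rates, RAND with f = 10%** (without the futility stop): 94% at 89/89 and 86% at 89/87. With the control rate of 89.7% cited in Protocol 1.1.2.1 and OCTAPLEX at 85%, RAND power is 69% and mITT power 76%.

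**Interim.** RAND would have about 92 per arm (185/2) at the interim and 185 at the end, against 83 and 166 in the table. Both interims are at half, so the boundaries stand. The chance of an efficacy stop at 89/85 is 38% on mITT and 32% on RAND with f = 10%.

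**Error rate.** At the RAND null for f = 10% (80.1% against 65.1%) the test rejects 2.5% of the time. A difference of 15 points in RAND equals 15/(1 − f) points among mITT patients: 15.8, 16.7 and 17.6 at 5%, 10% and 15%. A true 15-point deficit among mITT patients (89 against 74) therefore passes the RAND test 3.6%, 5.0% and 6.6% of the time. That is a different null hypothesis, not inflation of the plan's type I error.

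**The case against.** - **Nothing is miscalculated, and the text ties 166 to mITT.** Both true. The fault is a mismatch of populations: no power is given for the test that decides the trial.
- **89/85 is called conservative.** With the full 10% scored as failures, RAND power is 80.3% at 89/86, so the shortfall is worth one percentage point in one assumed rate. This stands as context, but 89/85 with 10% is the scenario the plan itself uses.
- **The rates may have been meant for all randomised patients.** RAND power would then be 84-85%. But the plan ties 166 to mITT, and on this reading the 10% allowance would have no purpose.
- **The loss depends on how non-operation varies.** With exactly 19 scored failures in each arm, power is 77.7%. That is milder, but still below 80.3%.
- **The 89.7% control rate is secondary.** It comes from 87 subjects, and holding OCTAPLEX at 85% widens the deficit to 4.7 points. The plan's table already shows the sensitivity, with 193 per arm at 90/85. This is fair; the main result does not rest on it.
- **The interim effect is small.** For a true 89/74 with 10% scored failures, the chance of passing at the interim alone is 1.8% on RAND against 1.0% on mITT. SAP 12.4 lists relevant individual data, authorities are consulted before stopping, and a full final analysis follows. All true. It limits the harm, but does not explain why an available and already planned comparison is left out.

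**Conclusion.** The concern holds. Under the plan's own assumptions (89% against 85%, 10% not treated or operated on), the primary RAND test has about 73% power, roughly 7 points below the stated 80.3%. At 89/85 the stated figure is reached only if about 3% or fewer are scored as failures.

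This assumes that 89% and 85% describe mITT patients, and that each patient in either arm has the same independent chance of being scored as a failure for not being treated or operated on. Rescue coagulation treatment, also scored as failure, is not modelled.

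The consequence is mainly a higher risk of failing to show non-inferiority. The RAND test keeps its 2.5% error on its own hypothesis. This should be fixed, but it does not invalidate the design.

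**What to change.** 1. In Protocol 9.1 and SAP 3.1, state that 80.3% is the power of the mITT analysis, and give the RAND power: about 81%, 78%, 73% and 69-70% at 3%, 5%, 10% and 15% scored failures. Note that the 89% control assumption is slightly below the cited 89.7% (RAND power about 69% at 89.7/85 with 10%).
2. In the SAP 12.4 table, label 83 and 166 per arm as mITT, or add the RAND numbers (about 92 and 185).
3. Add the mITT test of the primary endpoint to the interim package in SAP 12.5, as supporting information. The stopping rule stays on RAND.

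The primary test, boundaries, sample size and imputation rules stay as they are. The cost is wording, plus one interim run of a test already planned for the final analysis; no extra patients are needed. A change to Protocol 9.1 goes through the amendment process in Protocol 10.4. The price for the sponsor is a less favourable stated power for the primary analysis.

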3.2 Randomization, blinding and unblinding procedures

Randomization will be implemented by site staff using an IRT system. Randomization allocation will be 1:1 to OCTAPLEX or Beriplex[®] P/N (Kcentra), respectively.

Patients receiving a VKA generally have an underlying higher risk of thromboembolic events (TEEs), the reason for administration of the antagonist. Withdrawal of the antagonist and restoration of coagulation via administration of prothrombin complex concentrates (PCC) can therefore raise the risk of TEEs, with the risk being more pronounced in those patients who have experienced TEEs in the past. To balance this factor that may impact on safety comparisons between the treatment groups, randomization will be stratified by 'History of TEE (yes/no)'.

As the type of surgery and expected blood loss volume may impact on efficacy comparisons Expected blood loss ("≥200 mL", "≥100 mL but <200 mL" or "≥50 mL but <100 mL")' and permission 'Type of planned surgery ("orthopaedic surgery", "cardiothoracic surgery" or "other surgery")' will be a further stratification factor.

Regarding expected blood loss:

- At least 40% of all patients enrolled will be scheduled for an urgent surgery with expected blood loss of ≥ 200 mL.
- At least 20% of all patients enrolled will be scheduled for an urgent surgery with expected blood loss of $\geq 100 \text{ mL}$ but < 200 mL.
- , be sch .u. . Histribu eroperty of Octapharma. Do not copy of distribut • At most 40% of all patients enrolled will be scheduled for an urgent surgery with

Analysis Populations 4

Enrolled Analysis Population

The enrolled analysis population includes all patients who provided informed consent.

Randomized Population (RAND)

The randomized population will include all randomized patients irrespective of whether they received treatment. Following the intent-to-treat principle all patients will be analysed according to the treatment group to which they were randomized. This is the intent-to-treat irmission. (ITT) population according to the most rigid definition of ITT.

Safety Analysis Population (SAF)

The safety analysis population (SAF) will include all randomized patients who received investigational medicinal product (IMP). Patients receiving different study treatments than originally randomized will be considered according to the treatment actually received (rather without than that of the original randomization).

Modified Intention-to-Treat Population (mITT)

The mITT population will consist of all randomized patients who received IMP, and who had the surgery initiated or for whom the surgery was not initiated for medical reasons related to ordist insufficient coagulation.

Per Protocol Population (PP)

The PP population will consist of all those patients in the mITT population, excluding patients with major protocol deviations potentially affecting the primary endpoint. The following patients will be excluded:

- Patients who receive an IMP different to the IMP assigned by randomization •
- Patients who receive less than 70% of the planned dose •
- Patients who significantly violate inclusion/exclusion criteria
- Patients with missing primary efficacy assessment •
- Start of surgery more than 5 hours after end of infusion of IMP

A final decision about the classification of protocol deviations as major and minor and their consequences regarding assignment of patients to analysis populations will be made during the blinded data review meetings prior to unblinding of patient cohorts for the interim and final analyses. Decisions and outcome will be approved by the Sponsor.

All patients excluded from the different analysis populations will be listed together with the reason for exclusion. The listing will also be presented by study site.

All safety analyses will be based on the SAF population. The primary efficacy analysis will be based on the RAND population.

Furthermore, additional efficacy analyses will be performed using the mITT and the PP populations, as specified in section 10 Efficacy. Demographic and background characteristics will be presented on the SAF, RAND and mITT. In case of only minor differences between

any analysis set, it will be discussed during the blind data review meeting to omit the creation of individual sets and use the next available set for the given analyses.

If not otherwise stated in the respective section, the statistical analyses will be performed for the following analysis populations:

| Analyses | RAND (ITT) | | mITT | PP | SAF |
|---|--------------|---|-------|--------|--------------|
| Demographics and background characteristics | ~ | | | | \checkmark |
| Exposure and compliance | \checkmark | | | | · |
| Previous and concomitant therapies | ✓ | | | | rmissie |
| Surgery information | ✓ | | | ~~ P | 0. |
| Efficacy: Primary | \checkmark | | ✓ | Vitte. | |
| Efficacy: Secondary | \checkmark | | الى ٧ | V | |
| Efficacy: Exploratory | \checkmark | | aitho | | |
| Efficacy: Subgroup analysis | \checkmark | 1 | S | | |
| property of Octapharma. Do n | ot copy or d | | | | |

5 General Statistical Methods and Definitions

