# 9.2.2 In addition the primary endpoint will also be analysed using the mITT and the PP population. Efficacy Analysis Plan

### 9.2.2.1 Primary Endpoint: Hemostatic Efficacy

The primary efficacy variable is the hemostatic efficacy as assessed by the IEAB. The hemostatic efficacy is to be assessed based on objective criteria in the categories 'excellent', 'good', 'moderate' or 'none'. Ratings of 'excellent' and 'good' will be considered as 'effective' hemostasis, while a rating of 'moderate' and 'none' will be considered as 'ineffective' hemostasis.

The dichotomous 'hemostatic success' variable will be used in the analyses. This variable will be imputed as 'ineffective' under the following two circumstances:

- If hemostatic efficacy value is missing, then hemostatic efficacy will be considered 'none' for the analysis. This can occur in the RAND population if the patient is randomized and not treated (or does not undergo surgery), also in the mITT population if the patient is treated but does not undergo surgery due to insufficient coagulation.
- If patient receives additional coagulation treatment (e.g. PCC, single coagulation factors, plasma) after initial IMP infusion, then hemostatic efficacy will be considered 'none' for the analysis.

To demonstrate that treatment with OCTAPLEX is clinically not inferior to treatment with Beriplex® P/N (Kcentra) with respect to hemostatic success, a two-sample, one-sided test of the pair of hypotheses:

H0: 
$$p_K - p_O \ge \delta$$
 (inferiority)  
vs. H1:  $p_K - p_O < \delta$  (non-inferiority)

will be carried out with a type I error probability of  $\alpha = 0.025$  and clinical non-inferiority margin of  $\delta = 0.15$ . Whereby  $p_0$  and  $p_K$  present the probabilities of hemostatic success of OCTAPLEX and Beriplex® P/N (Kcentra) respectively.

Farrington's and Manning's test for difference in proportions will be used to assess the primary hypothesis in an interim and in the final analysis. One-sided p-values and the corresponding nominal and repeated CIs for the difference in hemostatic success probabilities will be presented.

The primary analysis will be performed on the RAND population. Additional analyses will be performed for the mITT and the PP population.

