In case of non-inferiority in the RAND, mITT and the PP population a "tipping point" analysis will be done to determine the robustness of the results. Iteratively patients excluded from the RAND/mITT/PP analysis assigned to the control arm will be considered as treatment successes, and patients excluded from the RAND/mITT/PP analysis and assigned to the OCTAPLEX arm will be considered as treatment failures, to determine the number of such imputed outcomes required to "tip" the study result from positive to negative in the randomized population.

A sensitivity analysis will be conducted in the RAND, mITT, and PP populations based on the hemostatic efficacy rating by the investigators at the end of surgery.

A concordance analysis will be done to assess the agreement between the assessment by the IEAB and the investigator assessment.

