#### 9.2.4 Handling of Missing Data

In general, missing data will not be imputed.

Patients for whom the primary efficacy endpoint 'hemostatic success' can't be assessed will be considered as having clinical hemostasis rated as "none". This efficacy analysis is performed with the RAND population (as primary), and additionally with the mITT and PP.

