Patients with missing information on the primary efficacy endpoint (for example, patient for whom the surgery was not initiated due to an insufficient coagulation), will be assessed as having no hemostasis (i.e., hemostatic efficacy will be considered 'none' for the analysis).

Sensitivity and Robustness Analyses

In order to assess the treatment effect using different assumptions from those in the RAND analysis, the primary efficacy analysis will also be performed using the mITT and PP populations.

In case of non-inferiority in the mITT and the PP populations a "tipping point" analysis will be done to determine the robustness of the results

Iteratively patients excluded from the mITT/PP analysis assigned to the control arm will be considered as treatment successes, and patients excluded from the mITT/PP analysis and assigned to the OCTAPLEX arm will be considered as treatment failures, to determine the number of such imputed outcomes required to "tip" the study result from positive to negative 3 in the RAND population.

A sensitivity analysis will be conducted in the RAND, mITT, and PP populations based on the hemostatic efficacy rating by the investigators at the end of surgery. This analysis will be conducted with the same methods as described above for the primary efficacy endpoint.

A concordance analysis (hemostasis agreement) will be done to assess the agreement between the assessment by the IEAB and the investigator assessment.

the assessment by the IEAB and the investigator assessment. **10.2 Secondary efficacy analyses** The secondary efficacy endpoints will be tested for differences between OCTAPLEX and Beriplex[®] P/N (Kcentra). No confirmatory hypotheses testing will be done. Treatment will be compared exploratorily, point estimates and corresponding 95% confidence intervals will be presented in addition to descriptive statistics.

The following measurements will be considered as exploratory secondary endpoints:

- Proportion of patients with an INR value of less or equal to 1.5 at 30 (\pm 15) minutes after the end of infusion.
- Change in coagulation factor levels from baseline to 30 (\pm 15) minutes after the end of infusion:
 - 0 Factor FII
 - Factor FVII
 - Factor FIX
 - Factor FX
- Proportion of patients receiving red blood cells (RBC) during the surgery

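### Read literally, the per-protocol rule on missing ratings removes patients whose surgery was not started for insufficient coagulation, although mITT counts them as failures; the primary analysis is not affected

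*SAP*

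**What the plan says.** **PP set.** SAP Section 4 and Protocol 9.2.1 define PP as mITT minus patients with major deviations that could affect the primary endpoint. The list of exclusions includes "Patients with missing primary efficacy assessment", with no exemption.

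**mITT set.** Both documents keep treated patients whose surgery was not started for medical reasons related to insufficient coagulation. Protocol 9.2.1 fixes their outcome: "whereas patients in whom the surgery was not initiated for coagulation-related reasons will be considered as treatment failures".

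**Missing ratings.** Protocol 9.2.2.1 states: "If hemostatic efficacy value is missing, then hemostatic efficacy will be considered 'none' for the analysis". Both documents say that this can arise "also in the mITT population if the patient is treated but does not undergo surgery due to insufficient coagulation". Under its missing-data heading, SAP 10.1 gives as its example of missing endpoint information a patient for "whom the surgery was not initiated due to an insufficient coagulation". Protocol 9.2.4 says of the missing-equals-'none' analysis: "This efficacy analysis is performed with the RAND population (as primary), and additionally with the mITT and PP".

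**Tipping point.** SAP 10.1 starts it "In case of non-inferiority in the mITT and the PP populations a" tipping-point analysis is done; Protocol 9.2.2.1 also requires non-inferiority in RAND. Protocol 9.2.2.1 describes the recoding: "Iteratively patients excluded from the RAND/mITT/PP analysis assigned to the control arm will be considered as treatment successes", with excluded OCTAPLEX patients set to failure. SAP 10.1 has the same rule for mITT and PP exclusions.

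**The concern.** A patient who received the product and could not be operated on because coagulation was still insufficient is a treatment failure, not a protocol deviation. The SAP calls that patient's rating missing, and PP excludes missing ratings, so the rule as written selects on outcome. In a non-inferiority trial PP is meant to corroborate the primary result, and it does this less well if it omits failures that mITT counts.

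The consequences go a little beyond the PP primary comparison:

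- The PP version of the investigator-rating analysis (SAP 10.1) loses the same patients.
- So do the PP versions of the INR and coagulation-factor endpoints (SAP 10.2). The red-cell endpoint is already limited to patients who undergo surgery.
- The tipping-point analysis depends on PP for its trigger and for part of its patient pool. A control patient who is a failure in mITT could be recoded there as a success, which works against OCTAPLEX.

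**Working it through.** **1. Reading the rules together.** Take a treated patient whose surgery was not started for insufficient coagulation.

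| Set or rule | Source | Result |
|---|---|---|
| RAND | Protocol 9.2.2.1, SAP 10.1 | in, 'none' |
| mITT | Protocol 9.2.1, SAP 4 and 10.1 | in, failure |
| Is the rating missing? | SAP 10.1 | yes, by its own example |
| PP | Protocol 9.2.1, SAP 4 | out, because missing |
| Missing = 'none' in PP | Protocol 9.2.4 | named, but nothing left to act on |

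**2. Inputs.** From SAP 3.1: margin 0.15, success rates 89% (control) and 85% (OCTAPLEX), 166 per arm. From SAP 12.4: boundaries 2.33216 at 83 per arm and 2.07753 at 166 per arm. The share f of non-starts for insufficient coagulation is not in the documents. I assume 0 to 5% per arm; 3% of 166 is about 5 patients and 5% about 8.

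**3. The plan's own figure.** The Farrington-Manning statistic is z = (0.15 − (p̂K − p̂O)) / √(p̃K(1−p̃K)/nK + p̃O(1−p̃O)/nO), where p̃K and p̃O are the maximum-likelihood estimates under a difference of 0.15. Simulating the two-stage design at 89% versus 85% with the SAP boundaries gives power of 80.4% with the futility stop applied and 80.5% without. The plan states 80.3%, so it reproduces.

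**4. Single data sets.** There are 166 per arm in mITT, and patients who are not non-starts succeed at about 89% (control) and 85% (OCTAPLEX).

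| Non-starts, control / OCTAPLEX | mITT | PP, read literally |
|---|---|---|
| 0 / 5 | 148/166 − 137/166 = 0.066; z = (0.15 − 0.0663)/0.0392 = 2.14 | 148/166 − 137/161 = 0.041; z = (0.15 − 0.0406)/0.0390 = 2.80 |
| 0 / 8 | 148/166 − 134/166 = 0.084; z = 1.65, fails | 148/166 − 134/158 = 0.043; z = 2.71, passes |
| 5 / 5 | 143/166 − 137/166 = 0.036; z = 2.78 | 143/161 − 137/161 = 0.037; z = 2.87 |

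**5. Pass rates at the final boundary.** Let X be successes, X ~ Bin(166, p), and let M be non-starts among the failures, M ~ Bin(166 − X, f/(1 − p)). mITT uses X/166 and PP uses X/(166 − M). The true PP difference is pK/(1 − fK) − pO/(1 − fO). With 3% in OCTAPLEX only it is 0.89 − 0.74/0.97 = 0.127, below the margin of 0.15. Exact enumeration at the margin (89% versus 74%) gives:

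| f control / f OCTAPLEX | True PP difference | mITT passes | PP passes |
|---|---|---|---|
| 0 / 0 | 0.150 | 1.9% | 1.9% |
| 0 / 2% | 0.135 | 1.9% | 4.2% |
| 0 / 3% | 0.127 | 1.9% | 6.2% |
| 0 / 5% | 0.111 | 1.9% | 12.5% |
| 1% / 3% | 0.136 | 1.9% | 4.0% |
| 2% / 3% | 0.145 | 1.9% | 2.4% |
| 3% / 3% | 0.155 | 1.9% | 1.4% |
| 3% / 0 | 0.178 | 1.9% | 0.3% |

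mITT and PP together pass no more often than mITT alone, so never above 1.9%.

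At the planning rates (89% versus 85%) mITT passes 79.5%. PP passes 94.8% with 3% in OCTAPLEX only, 84.1% with 3% in both arms, and 57.4% with 3% in control only.

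These rates describe one supportive analysis at a single look. They are not the trial's error rate.

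**The case against.** **The blinded review will settle it.** PP is framed around protocol deviations, and a non-start for insufficient coagulation is an outcome. Protocol 4.5 handles deviations individually, and SAP Section 4 leaves final assignment to a blinded meeting. A sensible meeting could keep these patients. This stands as mitigation. But neither document tells the meeting to do so, and the listed exclusion points the other way.

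**The group is small.** Protocol 4.2.3 allows further pre-operative coagulation treatment. A patient who receives it and is then operated on has a rating, is imputed 'none' and stays in PP. This stands, and it is why the figures above are only illustrations.

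**There is no established direction.** A reader might infer that the rule favours OCTAPLEX. The documents do not support that. At the margin PP is more lenient only if OCTAPLEX has more such patients; with equal rates it is slightly stricter. A marked imbalance is also unlikely if the products perform alike. At a shared rate of 2%, five or more in OCTAPLEX with none in control has probability of about 0.24 × 0.035 = 0.8%.

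**The trial's error rate.** A reader might infer that the chance of a false claim of non-inferiority rises. It does not. The primary test and the interim decision use RAND, where these patients count as failures, and no decision rule rests on PP alone.

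**The tipping-point analysis repairs it.** A reader might infer that returning the excluded patients restores the mITT result. The planned analysis does something else. It tips the result in the randomized population, where patients excluded from mITT are also recoded, and it reports how many imputed outcomes are needed rather than a pass or fail. It also runs only once PP has passed.

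**The distortion would be visible.** SAP Section 4 lists exclusions with reasons, and SAP 6.1 tabulates them by arm. That is true, but visibility does not correct the set.

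**Conclusion.** The inconsistency is in the text and the concern holds at a minor level. As written, PP removes patients whom mITT counts as failures, on account of their outcome, and Protocol 9.2.4 does not fit with that exclusion. What is affected is the PP primary analysis, the PP investigator-rating analysis, the PP INR and factor-level analyses, and the trigger and pool of the tipping-point analysis.

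The size depends wholly on an unstated frequency and on imbalance between arms. Over the assumed range of 0 to 5%, the PP pass rate at the margin runs from 0.3% to 12.5%, against about 1.9% in mITT. Confidence is high on the reading of the text and low on the practical size.

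**What to change.** - **SAP Section 4 and Protocol 9.2.1:** limit the PP exclusion to patients whose primary efficacy assessment is missing for reasons unrelated to insufficient coagulation. State that patients whose surgery was not started for insufficient coagulation stay in PP and are rated 'none', with the reason confirmed at the blinded data review.
- **Protocol 9.2.4 and SAP 10.1:** state that in PP the missing-equals-'none' rule applies to these patients only.

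Once they are no longer excluded, the tipping-point analysis has no reason to recode the control patients among them as successes. The cost is one or two sentences in each of the two population sections and one sentence in each of the other two. No new data are needed, because the reason for not starting surgery already decides mITT membership.
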